10.5. Appendix 5: Liver Safety: Suggested Actions and Follow-up Assessments

See Master Protocol CPMP Appendix 6 for liver safety: suggested actions and follow-up assessments.

10.6. Appendix 6: Provisions for Changes in Study Conduct During Exceptional Circumstances

Implementation of this appendix

The changes to procedures described in this appendix are temporary measures intended to be used only during specific time periods as directed by the sponsor in partnership with the investigator.

Exceptional circumstances

Exceptional circumstances are rare events that may cause disruptions to the conduct of the study. Examples include pandemics or natural disasters. These disruptions may limit the ability of the investigators, participants, or both to attend on-site visits or to conduct planned study procedures.

Implementing changes under exceptional circumstances

In an exceptional circumstance, after receiving the sponsor's written approval, sites may implement changes if permitted by local regulations.

After approval by local Ethical Review Boards, regulatory bodies and any other relevant local authorities, implementation of these exceptional circumstance changes will not typically require additional notification to these groups, unless they have specific requirements in which notification is required (for example, upon implementation and suspension of changes). All approvals and notifications must be retained in the study records.

If the sponsor grants written approval for changes in study conduct, the sponsor will also provide additional written guidance, if needed.

Considerations for making a change

The prevailing consideration for making a change is ensuring the safety of study participants. Additional important considerations for making a change are compliance with Good Clinical Practice, enabling participants to continue safely in the study and maintaining the integrity of the study.

Informed consent

Additional consent from the participant will be obtained, if required, for:

- participation in remote visits, as defined in Section "Remote Visits"
- dispensation of additional study intervention during an extended treatment period
- alternate delivery of study intervention and ancillary supplies, and
- provision of their personal or medical information required prior to implementation of these activities.

Changes in study conduct during exceptional circumstances

Changes in study conduct not described in this appendix, or not consistent with applicable local regulations, are not allowed.

The following changes in study conduct will not be considered protocol deviations.

Remote visits

Telemedicine: Telephone or technology-assisted virtual visits, or both, are acceptable to complete appropriate assessments.

Mobile healthcare: Healthcare visits may be performed by a mobile healthcare provider at locations other than the study site when participants cannot travel to the site due to an exceptional circumstance if written approval is provided by the sponsor.

Procedures performed at such visits include, but are not limited to, collection of blood samples, symptom-directed physical examinations, ECGs, vital signs, intervention accountability and compliance, AE collection, and collection of health information.

Other alternative locations: Laboratory draws may be done at an alternate location in exceptional circumstances.

In source documents and the CRF, the study site should capture the visit method, with a specific explanation for any data missing because of missed in-person site visits.

Regardless of the type of remote visits implemented, the protocol requirements regarding the reporting of AEs, SAEs, and PCs remain unchanged.

Every effort should be made to enable participants to return to on-site visits as soon as reasonably possible, while ensuring the safety of both the participants and the site staff.

Local laboratory testing option

Local laboratory testing may be conducted in lieu of central laboratory testing. The local laboratory must be qualified in accordance with applicable local regulations.

CCI

Study intervention and ancillary supplies (including participant diaries)

When a participant is unable to go to the site to receive study supplies during normal on-site visits, the site should work with the sponsor to determine appropriate actions. These actions may include:

- asking the participant to go to the site and receive study supplies from site staff without completion of a full study visit
- asking the participant's designee to go to the site and receive study supplies on a participant's behalf, and
- arranging delivery of study supplies.

These requirements must be met before action is taken:

Alternate delivery of study intervention should be performed in a manner that does
not compromise treatment blinding and ensures product integrity. The existing
protocol requirements for product accountability remain unchanged, including
verification of participant's receipt of study supplies.

- When delivering supplies to a location other than the study site (for example, participant's home), the investigator, sponsor, or both should ensure oversight of the shipping process to ensure accountability and product quality (that is, storage conditions maintained and intact packaging upon receipt).
- Instructions may be provided to the participant or designee on the final disposition of any unused or completed study supplies.

Adjustments to visit windows

Whenever possible and safe to do so, as determined by the investigator's discretion, participants should complete the usual Schedule of Activities as described in Master Protocol CPMP, CPMP(3) DSA, and NP05 ISA. To maximize the possibility that these visits can be conducted as on-site visits, the windows for visits may be adjusted, upon further guidance from the sponsor. This minimizes missing data and preserves the intended conduct of the study.

For participants whose visits have extended windows, additional study intervention may need to be provided to avoid interruption and maintain overall integrity of the study.

Documentation

Sites will identify and document the details of how participants, visit types, and conducted activities were affected by exceptional circumstances. Dispensing/shipment records of study intervention and relevant communications, including delegation, should be filed with site study records.

Source documents generated at a location other than the study site should be part of the investigator's source documentation and should be transferred to the site in a secure and timely manner.

	7.12.1.	Adverse Events	
	7.12.3.	Deaths, Other Serious Adverse Events, and Other Notable	
	_	Adverse Events	15

Page	3
------	---

	7.12.4.	Neurological Exam	15
	7.12.5.	Clinical Laboratory Evaluation	15
	7.12.6.	Vital Signs and Other Physical Findings	16
	7.12.7.	Electrocardiograms	16
	7.12.8.	Suicidal Ideation or Behavior	16
7	.13. Sub	ogroup Analyses	16
7	.14. Pro	tocol Deviations	16
7	.15. Inte	erim Analyses and Data Monitoring	16
7	.16. Pla	nned Exploratory Analyses	17
7	.17. Tot	ality of Evidence for Efficacy	17
7	.18. Tot	ality of Evidence for Safety	18
7	.19. Anı	nual Report Analyses	18
7	.20. Clii	nical Trial Registry Analyses	19
8.	Unblin	nding Plan	20
9.	Refere	nces	21

3. Abbreviations and Definitions

[figure not shown]
Term	Definition
AE	adverse event
ALT	alanine aminotransferase
API	average pain intensity
AST	aspartate aminotransferase
BPI-SF	Brief Pain Inventory-Short Form
вма	Bayesian model averaging
cLDA	constrained longitudinal data analysis
compliance	Adherence to all study-related, good clinical practice (GCP), and applicable regulatory requirements.
CPMP	H0P-MC-CPMP
CTR	Clinical Trial Registry
ECG	electrocardiogram
eCOA	Electronic Clinical Outcome Assessment
eGFR	estimated glomerular filtration rate
enroll	The act of assigning a participant to a treatment. Participants who are enrolled in the study are those who have been assigned to a treatment.
FDA	United States Food and Drug Administration
FMQ	FDA Medical Query
GFR	glomerular filtration rate
ISA	intervention-specific appendix
LLT	Lowest Level Term
LY	LY3857210
MedDRA	Medical Dictionary for Regulatory Activities
MMRM	mixed-effect model for repeated measures
NP05	H0P-MC-NP05
NRS	numeric rating scale

Term	Definition
participant	Equivalent to CDISC term "subject": an individual who participates in a clinical trial, either as recipient of an investigational medicinal product or as a control
PDEP	preliminary data entry period
PK/PD	pharmacokinetics/pharmacodynamics
CCI	
РТ	Preferred Term
PTEAE	posttreatment-emergent adverse event
QTcF	Fridericia's corrected QT interval
SAP	statistical analysis plan
SMQ	standardized MedDRA query
TEAE	Treatment-emergent adverse event: An untoward medical occurrence that emerges during a defined treatment period, having been absent pretreatment, or worsens relative to the pretreatment state, and does not necessarily have to have a causal relationship with this treatment.
ТоЕ	totality of evidence
ULN	upper limit of normal
VAS	visual analog scale

4. Revision History

SAP Version 1 was approved on 19 January 2023 prior to unblinding data for Study H0P-MC-NP05 (NP05).

SAP Version 2 was approved prior to unblinding data for final lock. Major revisions included:

• Section 7.12.3: change SMQ to FMQ, which is FDA new standard.

• Section 7.18: added seizures in the totality of evidence of safety.

5. Study Objectives

5.1. Primary Objective

The primary objective of this ISA is stated in the Study H0P-MC-CPMP (a) protocol. See Section 7.10.1 for more details on the primary analysis method. For Study NP05, endpoint is defined as 8 weeks post initial treatment administration at Visit 7. Unless otherwise specified, the time point for secondary endpoint measurements is the same as the primary endpoint.

5.2. Secondary Objectives

Secondary objectives applicable to all ISAs are listed in the Study CPMP SAP Version 5.

Additional secondary endpoints specific to Study NP05 are listed in Table NP05.5.1.

 Table NP05.5.1.
 Additional Secondary Endpoints Specific to Study H0P-MC-NP05

Objective	Endpoint Measure	
Other Secondary		
Physical Functioning Efficacy of LY3857210 versus placebo	Mean change from baseline to endpoint for the Brief Pain Inventory-S Form (BPI-SF) for the mean interference score mean severity score individual severity scores, and individual interference scores Proportion of participants with reduction from baseline greater than or equal to 30%, 50%, and 70% on BPI-SF for the mean interference score mean severity score individual severity scores, and	
	 individual interference scores. 	

5.3. Exploratory Objectives

The following exploratory objectives and endpoints are specific to Study NP05 are shown in Table NP05.5.2.

Table NP05.5.2. Exploratory Objectives/Endpoints Specific to Study H0P-MC-NP05

[figure not shown]

6. Study Design

6.1. Summary of Study Design

The Study CPMP protocol provides a summary of the overall study design for the chronic pain master protocol. ISA-specific study design is provided in the NP05 protocol.

6.2. Determination of Sample Size

CCI

If there is no treatment

difference between placebo and LY3857210, the probability of passing the primary objective specified above (that is, false positive rate) is approximately 0.067. The simulation for the power calculation and sample size determination was carried out using the R package simfast v1.3.0.9000.

6.3. Method of Assignment to Treatment

The method of treatment assignment is described in the CPMP SAP Version 5.

7. A Priori Statistical Methods

7.1. General Considerations

The estimand for the primary clinical question of interest has been described in the CPMP SAP Version 5

Unless otherwise specified, efficacy and safety analyses will be conducted for the 8-week double-blind period and separately for the entire 10-week study period.

Other general considerations for analyses are described in the CPMP SAP Version 5.

7.2. Adjustments for Covariates

The general adjustment strategy has been described in the CPMP SAP Version 5.

7.3. Handling of Dropouts or Missing Data

The missing data strategy has been described in the CPMP SAP Version 5.

7.4. Multiple Comparisons/Multiplicity

There is no plan to formally adjust for multiplicity.

7.5. Use of an "Efficacy Subset" of Participants

There are no plans to use a modified efficacy subset.

7.6. Participant Disposition

The summary of participant disposition has been described in the CPMP SAP Version 5.

7.7. Participant Characteristics

The summary of participant characteristics has been described in the CPMP SAP Version 5.

ISA-specific considerations are described below.

- Michigan Neuropathy Screening Instrument
 - o Part A history subscale ($<7 \text{ vs.} \ge 7$)
 - o Part B physical assessment subscale ($<3 \text{ vs.} \ge 3$)

7.8. Treatment Compliance

Treatment percentage of compliance will be calculated as:

$$\frac{\textit{Total pills taken}*100}{\textit{Total pills expected}}\%$$

with total pills taken calculated by total pills dispensed minus total pills returned. A patient is considered to be compliant for a given period if this percentage is between 80% and 120%. Treatment compliance will be assessed at Visits 5 and 7 (and early discontinuation visit, if applicable); at Visits 4 and 6, the investigational product will not be returned to the site.

Treatment compliance will be reported for the 8 weeks of the treatment period (Visits 3 to 7). The percentage of patients who are compliant with study drug will be summarized by treatment group. For patients who discontinue early, time after the penultimate visit will be excluded for calculation of treatment compliance. For example, if patient discontinued early at Visit 6, treatment compliance will be derived only from data collected through Visit 5. Comparisons between treatment group for treatment compliance will be performed using a Fisher's Exact test. Listings for treatment compliance of individual patients by treatment period will also be provided.

Depending on the level of observed treatment compliance, and where appropriate, sensitivity analyses of primary endpoints may be conducted by excluding patients with poor treatment compliance.

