1.3. Schedule of Activities (SoA)

This SoA shows visits and procedures unique to the intervention-specific appendix (ISA) H0P-MC-NP05 for LY3857210. Please refer to Master Protocol CPMP and the DPNP DSA CPMP(3) SoAs for additional information.

	Scre	ening	Randomiza tion to ISA			Double-Blind Treatment			F/U	Notes
	V1	V2	V3	V4	V5	V6	V7	ED	V801	
Study Week	Up to -6 months	-10 to -7 days for most participants	0	2	4	6	8		+2	
Visit Window (days)					±	:3			±3	
Confirm ISA inclusion and exclusion criteria	X	X	X							
Physical examination			X		X		X	X	X	Physical examination (see Section 8.2.1). Complete physical examination, including targeted examination specified below, should be performed at V3 and V801 or ED. Targeted physical examination for skin, gastrointestinal tract, mammary gland in males, and lymph nodes should also be performed at V5 and V7.
Neurological assessment			X	X	X	X	X	X	X	See Section 8.2.1.
Prespecified DPNP medical history			X							Includes diagnosis and symptom onset date.
Vital signs			X	X	X	X	X	X	X	At V3, vitals should be taken predose. Pulse rate, respiratory rate, blood pressure, and temperature taken with participant in a sitting position.
Concomitant medication									X	See footnote a.
AE									X	See footnote a.
ECG (single)					X		X	X	X	

form.

X

X

See footnote a.

See footnote a.

Review eDiary compliance.

Review assessment of pain. See MoO for additional details.

NRS for pain

Reinforce pain

reporting

assessment guidelines

Rescue medication usage

	Scre	ening	Randomiza tion to ISA			e-Blind tment	l		F/U	Notes
	V1	V2	V3	V4	V5	V6	V7	ED	V801	
Study Week	Up to -6 months	-10 to -7 days for most participants	0	2	4	6	8		+2	
Visit Window (days)					+	3			±3	
Placebo response video training (participant)		X								Should view at the beginning of V2.
Study intervention administration			X	X	X	X				See Section 6.1. Participant should be instructed NOT to take study intervention on the day of V7.
Dispense study intervention to participant			X	X	X	X				
Participant returns unused study intervention				X	X	X	X	X		Participant to bring study intervention to every visit.
Intervention compliance				X	X	X	X	X		
Scales, Questionnaires, an	nd Outcome M	easures	l	l	 	 	_	_		I
CCI										
C-SSRS Since Last Visit									X	See footnote a.
Self-Harm Supplement form									X	See footnote a.
Self-Harm Follow-Up form									X	See footnote a. Complete 1 form for each event identified on the Self-Harm Supplement

X

X

X

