X

[figure not shown]
X

X

	Scre	ening	Randomiza tion to ISA	Double Billia							F/U	Notes
	V1	V2	V3	V4	V5	V6	V7	ED	V801			
Study Week	Up to -6 months	-10 to -7 days for most participants	0	2	4	6	8		+2			
Visit Window (days)					±	:3			±3			
PGI									X	See footnote a.		
Clinical Laboratory Tests	s and Sample C	Collection										
Hematology				X	X	X	X		X			
Chemistry				X	X	X	X		X			
Lipid panel				X	X	X	X		X			
Urinalysis							X		X			
Urine pregnancy			X	X	X	X	X	X		For all WOCBP at V3: collect sample within 24 hours prior to dosing.		
Urine drug screen			X		X		X	X		See Section 5.3.1.		
HbA1c			X				X	X				
HbA1c			X				X	X		A4 V/2 - DIV1 -1111 - 4-1		
LY3857210 PK sample			X	X	X	X	X	X		At V3, a PK sample should be taken any time after 1 hour postdose and prior to leaving the site. At V4, V5, V6, V7 and ED, a PK sample can be taken at any time during the site visit. The date and time of each PK sample collected will be recorded. The date and time of LY3857210 administration prior to the PK sample collection will be recorded.		
CCI												

	Screening Randomiza tion to ISA		Randomiza tion to ISA		Double Treat	e-Blind ment			F/U	Notes
	V1	V2	V3	V4	V5	V6	V7	ED	V801	
Study Week	Up to -6 months	-10 to -7 days for most participants	0	2	4	6	8		+2	
Visit Window (days)					±3			±3		

Participant Devices

Abbreviations: AE = adverse event; CCI ; DPMP = diabetic peripheral neuropathic pain; ECG = electrocardiogram; ED = early discontinuation; F/U = follow-up; HbA1c = hemoglobin A1c; ISA = intervention-specific appendix; MoO = Manual of Operations; NRS = numeric rating scale; PGI = patient's global impression of change; PK = pharmacokinetic; V = visit; WOCBP = women of childbearing potential.

a Collect in addition to schedule described in Master Protocol CPMP.

2. Introduction

This ISA, H0P-MC-NP05 (NP05) is an appendix to Master Protocol H0P-MC-CPMP (CPMP) and contains unique study elements specific for LY3857210. The master protocol contains the overarching study elements that govern the DPNP DSA CPMP(3) and this ISA NP05.

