6.4. Study Intervention Compliance

When participants self-administer study intervention(s) at home, compliance with study intervention will be assessed at each visit. Compliance will be assessed by direct questioning and counting returned capsules and documented in the source documents and CRF. A record of the number of study intervention capsules dispensed to and taken by each participant must be maintained and reconciled with study intervention and compliance records. Intervention start and stop dates will also be recorded in the CRF.

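### SAP 7.8 counts capsules not handed back as taken and does not use the capsules-taken record required by Protocol 6.4, so some participants who stop dosing can be classed as compliant

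*SAP*

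**What the plan says.** SAP 7.8 defines compliance as 100 times pills taken over pills expected, "with total pills taken calculated by total pills dispensed minus total pills returned". The denominator, "Total pills expected", is not defined further. A percentage from 80 to 120 counts as compliant. Compliance is assessed at Visits 5 and 7 and at early discontinuation; "at Visits 4 and 6, the investigational product will not be returned to the site". For early discontinuers, the time after the penultimate visit is left out, and the SAP's own example scores a Visit 6 discontinuation on data through Visit 5. The results feed a by-arm summary, a Fisher's Exact test and individual listings. Depending on the compliance observed, "sensitivity analyses of primary endpoints may be conducted by excluding patients with poor treatment compliance".

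Protocol 6.4 describes a fuller assessment: "Compliance will be assessed by direct questioning and counting returned capsules and documented in the source documents and CRF". It also requires a per-participant record of capsules dispensed and capsules taken, to be reconciled with the compliance records, and it has intervention start and stop dates entered in the CRF. The Schedule of Activities (Protocol 1.3) marks product return and a compliance check at Visits 4, 5, 6, 7 and early discontinuation, with the note "Participant to bring study intervention to every visit".

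**The concern.** Dispensed minus returned equals taken only if every unused capsule comes back. A supply that is lost, forgotten or kept adds nothing to the returned count, so on the wording of SAP 7.8 all of it counts as swallowed. The people most exposed to this error are those who stopped dosing but kept attending. The protocol already asks sites for the information that would correct it, yet the SAP derivation does not use it.

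At stake is the credibility of the adherence figures in a proof-of-concept trial. A compliance-based sensitivity analysis, if run, could keep people who had stopped taking drug, which is the opposite of its purpose.

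**Working it through.** The documents give no compliance figure to reproduce, so the check applies the SAP formula to simple cases.

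**Inputs from the documents**
- Dosing is daily (Protocol 6.1). Capsules per dose are not stated but cancel in the ratio, so one unit below means one day's dose.
- The scored period is 8 weeks, Visits 3 to 7 (SAP 7.8): 8 × 7 = 56 units.
- Product is dispensed at Visits 3, 4, 5 and 6 (Protocol 1.3), two weeks apart: 4 × 14 = 56.

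**Assumptions, not in the documents**
- No spare capsules.
- Expected means planned days in the scored period.
- A supply that does not come back contributes zero to returned.

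**Formulas**
- Score = 100 × (dispensed − returned) / expected
- True = 100 × taken / 56

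**Case 1: stays in the study, stops at day 42**
- True: 42/56 = 75%, below the band.
- Remaining 14 returned: (56 − 14)/56 = 75%. The formula is right.
- Remaining 14 not returned: (56 − 0)/56 = 100%. Classed as compliant.

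**Case 2: stays in the study, returns correctly at Visit 5, does not return the Visit 5 to 7 supply**

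| Stop day | True | Returned at Visit 5 | Score | Class |
|---|---|---|---|---|
| 28 | 28/56 = 50% | 0 | 56/56 = 100% | compliant |
| 21 | 21/56 = 37.5% | 7 | 49/56 = 87.5% | compliant |
| 14 | 14/56 = 25% | 14 | 42/56 = 75% | not compliant |
| 7 | 7/56 = 12.5% | 21 | 35/56 = 62.5% | not compliant |

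The error is present in every row, but it changes the class only for the later stops.

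**Case 3: discontinues at Visit 5**

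By the penultimate-visit rule the score uses data through Visit 4. The SAP says nothing is returned at Visit 4, so the score is (14 − 0)/14 = 100% whatever was swallowed. No bottle needs to be lost; the result follows from the SAP's own rules whenever dispensed equals expected.

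**How far the result depends on the assumptions**
- Expected counted only to the stop date: in Case 1, with all 56 dispensed, the score is 56/42 = 133.3%, above the band and so not compliant.
- Spare capsules: the upper limit is 1.2 × 56 = 67.2, so the participant stays in the band only if spares total no more than 11.2 units, or 11.2/4 = 2.8 per 14-day interval (20%).
- Early discontinuation: an unreturned last supply falls in the excluded interval and adds nothing to the score.

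**The case against.** The best defence is that SAP 7.8 never says a missing return equals zero. It could be treated as missing, and SAP 7.3 leaves missing-data strategy to the CPMP SAP, which is not available here. Counting returned capsules is also one of the protocol's two methods, so the SAP does not contradict Protocol 6.4, and the dispensed and returned numbers may already have been reconciled before analysis. This stands in part: misclassification is conditional, not automatic. However, SAP 7.8 states its own arithmetic without referring elsewhere, and on that arithmetic an unreturned supply raises the score. Reconciled dispensing counts do not help if the taken value is not the one analysed.

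Three stronger readings are tempting, and the documents do not support them.
- **Anyone who stops dosing and keeps the bottle scores as fully compliant.** This fails for early discontinuers whose unreturned supply lies in the dropped last interval, for early stops in Case 2, and under the other definition of expected.
- **A null result could not be told apart from drug not taken.** Stop dates are in the CRF, SAP 7.12.1 summarises duration of exposure by arm, and plasma concentrations are reported across visits (SAP 7.11) from samples scheduled as follows: "At V4, V5, V6, V7 and ED, a PK sample can be taken at any time during the site visit". The pill count is not the only evidence of intake.
- **The 80% to 120% flag decides who is excluded from the sensitivity analysis.** The SAP refers only to poor compliance, does not tie it to that band, and makes the analysis optional.

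Nor do the documents show that adherent participants would be pushed above 120%: they give no figure for spare capsules.

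**Conclusion.** The point holds in a limited form. As written, the derivation can class a participant as compliant after a substantial part of the treatment period without drug: 75% true against 100% scored for a stop at day 42, and 37.5% against 87.5% in the less favourable pattern of Case 2. These figures rest on expected meaning planned days, spares of no more than 20% (none in the examples), an unreturned supply counted as zero, and that supply falling in a scored interval. The Visit 5 discontinuation result needs only dispensed equal to expected and the SAP's own return schedule.

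How many participants would be affected cannot be estimated from the documents. The reach is the by-arm compliance summary, the Fisher's Exact test, the listings and the optional sensitivity analysis. No primary analysis result changes. The conflict over returns at Visits 4 and 6 can be seen directly in the two documents and needs no assumption.

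**What to change.** Amend SAP 7.8 as follows:
- Compute pills taken from the reconciled capsules-taken record that Protocol 6.4 requires.
- Where a supply is not returned, use the recorded taken value or set that interval to unknown; do not count the supply as taken. Report the number of participants affected, by arm.
- Define the expected number, stating whether it runs over planned days or to the recorded stop date.
- Reconcile the statement that nothing is returned at Visits 4 and 6 with the protocol Schedule of Activities, and check that the penultimate-visit rule still works under whichever schedule applies.

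The cost is SAP wording and one small summary from data the protocol already requires. The downside is that a few participants will have unknown compliance and the reported rate may be slightly lower.

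### SAP 7.8 rules out drug return at Visits 4 and 6 although the protocol schedules it, which leaves early discontinuers with little or no usable compliance count

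*SAP*

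**What the plan says.** SAP Section 7.8 defines compliance as pills taken over pills expected, with pills taken equal to dispensed minus returned, and calls a participant compliant between 80% and 120%. On timing it says: "Treatment compliance will be assessed at Visits 5 and 7 (and early discontinuation visit, if applicable". It adds that "at Visits 4 and 6, the investigational product will not be returned to the site". For early discontinuers the rule is: "For patients who discontinue early, time after the penultimate visit will be excluded for calculation of treatment compliance". The SAP's example is that "if patient discontinued early at Visit 6, treatment compliance will be derived only from data collected through Visit 5".

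The protocol differs on return. In the Schedule of Activities (Section 1.3), the row "Participant returns unused study intervention" and the compliance row are both marked at V4, V5, V6, V7 and ED. Section 4.1 has participants bring all their bottles to each of V4 to V7. Section 6.4 says that "compliance with study intervention will be assessed at each visit", and on method: "Compliance will be assessed by direct questioning and counting returned capsules".

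**The concern.** A percentage built from dispensed minus returned pills exists only where a return is counted. The two documents disagree on whether that happens at V4 and V6. For completers this hardly matters, because V5 and V7 cover the treatment period. For early discontinuers it decides whether a value exists and how much treatment it covers, because the penultimate-visit rule already removes the last interval.

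The same SAP paragraph names the ED visit as a compliance assessment and then, through that rule, keeps its count out of the percentage. It does not say what the ED count is for.

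At stake are the percentage compliant by arm, the Fisher's exact test on it, and who would be left out if the optional sensitivity analysis excluding poor compliers is run.

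**Working it through.** The plan gives no figure to reproduce. The check applies the SAP rule to each return schedule.

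**Inputs.** Study weeks 0, 2, 4, 6 and 8 for V3 to V7 (protocol Section 1.3) give nominal days 0, 14, 28, 42 and 56, ignoring the visit window of plus or minus 3 days. Dosing is daily. The supplied text does not give capsules per day; one is assumed, and any constant number cancels from the ratio. Planned size is up to about 125, with 20% dropout (protocol Section 1.1).

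**Reading of the rule.** Since V801 follows the ED visit, the ED visit might itself be taken as the penultimate visit. The SAP's example rules this out: discontinuation at V6 uses data through V5.

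**Treated time without a usable count**, for discontinuation on day d, with the penultimate-visit rule kept in both cases:

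| Day d | SAP schedule: last usable count | Share dropped | Protocol counts: last usable count | Share dropped |
|---|---|---|---|---|
| up to 14 | none | undefined | none | undefined |
| 15–28 | none | undefined | V4 | (d−14)/d: 1/15 = 6.7% to 14/28 = 50.0% |
| 29–42 | V5 | (d−28)/d: 1/29 = 3.4% to 14/42 = 33.3% | V5 | same |
| 43–55 | V5 | (d−28)/d: 15/43 = 34.9% to 27/55 = 49.1% | V6 | (d−42)/d: 1/43 = 2.3% to 13/55 = 23.6% |

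So the V4 and V6 counts make a difference for discontinuation on days 15–28 and 43–55.

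**Can the classification change?** Take a participant who leaves after V6.

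- 28 of 28 capsules to V5, then 5 of 14 to V6: the SAP schedule gives 28/28 = 100%; with the V6 count it is 33/42 = 78.6%.
- 20 of 28, then 14 of 14: 20/28 = 71.4% against 34/42 = 81.0%.

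Both cross the 80% limit, in opposite directions. After full adherence to V5, the value with the V6 count is (28 + 14a)/42, where a is adherence from V5 to V6. It falls below 80% when a is under (0.80 × 42 − 28)/14 = 0.40.

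The same arithmetic applies to the SAP's own V6 example if the ED count were admitted and pills expected ran to V6. If drug stopped after the fifth capsule and pills expected ended there, the first case would be 33/33 = 100%.

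**How many.** 0.20 × 125 = 25 early discontinuers at the planned rate. Their timing is not given, so anywhere from none to all of them could fall in the undefined range. As illustration only, an even spread over 56 days would leave 25 × 28/56 = 12.5 without a value on the SAP schedule and 25 × 14/56 = 6.25 with the protocol's counts.

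**The case against.** The strongest reply concerns the penultimate-visit exclusion. It is a stated rule with a worked example, and a count can be taken at the ED visit for records and listings without entering the summary. There is a reason for caution too. With 28/28 to V5, five more capsules taken and a 14-capsule bottle never returned, the formula gives 42/33 = 127%. This stands: the exclusion is a choice, and what is missing is a statement of the ED count's purpose.

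A reader might infer that the protocol supplies a rival calculation. It does not. Section 6.4 covers collection and method and sets no percentage, limit or rule for early discontinuers. The conflict is over which counts will exist.

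The undefined range up to day 28 holds only if the SAP's schedule is followed. If sites follow the protocol, the V4 and V6 counts will be available. The classification examples were chosen to show that the limit can be crossed; they do not show a likely shift in either arm.

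Finally, SAP Sections 7.1 and 7.3 refer general and missing-data rules to the CPMP SAP, which was not supplied and may cover participants without a count. It would not remove the V4 and V6 conflict between the two NP05 documents.

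**Conclusion.** The conflict on drug return is direct, and as written the SAP leaves scheduled counts unused. Combined with the penultimate-visit rule, this gives no compliance value to participants who discontinue up to nominal day 28, where the protocol's counts would confine that to day 14. It drops 35% to 49% of treated time for those leaving on days 43–55, where the protocol's counts would drop 2% to 24%. These figures assume nominal visit days.

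The reach is limited. Completers can still be calculated. A reader might infer that the primary result is at risk; the supplied text does not support this, because the poor-compliance analysis is only optional. Nor does 20% dropout guarantee that about 100 participants are untouched, since it is a planning assumption that the trial could exceed. No direction of error can be claimed. The change should be made because it is cheap and the text is plainly inconsistent.

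**What to change.** 1. Reconcile the V4 and V6 return statement in SAP Section 7.8 with protocol Sections 1.3, 4.1 and 6.4, and calculate compliance from the counts scheduled at V4, V5, V6 and V7.
2. Either state that the ED count enters the percentage where product was returned, or keep the penultimate-visit rule and state that the ED count is for listing only.
3. Report by arm the number of participants with no usable count, unless the CPMP SAP already sets a rule for them.

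The cost is a few sentences and minor re-programming, using counts the protocol already schedules. If return at V4 and V6 was not in fact carried out, those counts will be missing and the reconciliation should say so. Compliance figures for early discontinuers may shift slightly in either direction.
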